2.7 Experimental Design

Our study will use glioma tissues, after all sampling for diagnosis will be collected. Moreover, we will take blood samples from patients undergoing surgery for HGGs and during the oncological follow-up. Tumor samples will be harvested in order to obtain parallel tumor cultures to test *in vitro* tumor sensitivity to different chemotherapies, with and without inhibition of V-ATPase. Moreover, we will analyze the expression of V-ATPase (especially subunit V1G1) in vesicles released by cancer cells, in order to understand how V-ATPase can influence drug resistance and tumor progression. HGG-released vesicles will be also isolated in the circulation from patients' blood in order to analyze tumor responses to oncological treatments and the genetic and epigenetic status of the tumor, including amplification of oncogenes (i.e. *c-Myc*), and the content of specific coding and non-coding RNA, DNA and retrotransposon elements, through the use of next generation sequencing (NGS)²⁸.

Duration for enrollment: 24months;

Duration for follow-up analysis: 12 months for each patient.

Maximum length of the study: 36 months including patients' follow-up

2.8 Withdrawal Criteria

The subject may withdraw at will at any time. The patient may be withdrawn from the trial at the discretion of the investigator for safety concerns. Patients who will meet the exclusion criteria after a prior inclusion in this study will be withdrawn. A patient withdrawn analysis will be made to clarify the related rate and possible impact on the study results.

STUDY NAME: Vacuolar ATPase and drug resistance of high grade gliomas: a study to investigate possible therapeutic roles for proton pump inhibitors. STUDY CODE: GLIODRUG-V	Ver. 1.0 07/06/2019
---	------------------------

2.9 Participating Units

Clinical data and collection of biological samples

ASST-Monza Ospedale San Gerardo

- U.O. di Neurochirurgia: Prof. [name]; Dr. [name]; Dr. [name]

Stem cell cultures and extraction of MVs

Università degli Studi di Milano Bicocca – Dipartimento di Medicina e Chirurgia

Laboratorio di Genetica Medica: Dr.ssa [name]

3 Materials and Methods

This study will evaluate patient data and biological tissues collected prospectively and anonymized prior to the analysis. The study protocol follows the ethical guidelines of the 1975 Declaration of Helsinki (as revised in Brazil 2013).

3.1 Clinical Variables collected

3.1.1. Anagraphic Data

Patient ID (anonymously assigned by the center in consecutive order); Date of Birth; Gender

3.1.2. Anamnestic Data

Karnopfsky Performance Status; ASA score; Previous Surgery

3.1.5 Pre-operative and post-operative radiological data

Tumor volume on pre- and post-operative brain MRI; extent of resection

3.1.6 Surgical Data

Date of surgery; location of the tumor; post-operative complications (e.g. hematoma, seizures)

3.1.7 Histopathological findings

Formal histological diagnosis with tumor grade and molecular classification according WHO 2016 classification of the tumors of the central nervous system.

3.1.8 Follow-up

Complications during adjuvant chemo-radiation therapy; treatment response; chemotherapy administered with number of cycles and dosage. Dose of radiations delivered. Time to tumor progression and overall survival.

3.2 Study supplies and products.

STUDY NAME: Vacuolar ATPase and drug resistance of high grade gliomas: a study to investigate possible therapeutic roles for proton pump inhibitors. STUDY CODE: GLIODRUG-V	Ver. 1.0 07/06/2019
---	------------------------

Patients will be treated according to local hospital procedure. No additional costs (materials, salaries, other) due to the study will be charged to the hospital. Study products will be those commonly used in the hospital according to the local rules.

3.3 Data handling

Data collection will be performed using an electronic database system, in accordance with the European Statement 679/2016/UE. The submitted data will be checked at San Gerardo Hospital (Monza) by clinicians (Neurosurgery Division) and by the the Medical Genetics Laboratory ([name]), of School of Medicine and Surgery, University of Milano-Bicocca. Once examined, the record will be accepted into the dataset for analysis.

3.4 Surgical methodology

Patients will be operated for intra-axial brain tumors. Part of the tumor specimen, will be sent for cell culture; while the majority of the tumor specimen will be used for a formal histological diagnosis. In order to achieve a gross total resection and confirm it histologically, a sample of marginal tissue of the surgical bed will be sent for cell culture and histology. Marginal tissue will be collected from non eloquent brain areas. Intraoperative ultrasound will be used to check presence or absence of high cellularity of the sample.

Patients with brain tumors other than gliomas at histological diagnosis will be excluded from the study. Sample of these tumors will be eliminated.

If the tissue removed from the patient enrolled in this study will not allow to perform the sample for the study without affecting the optimal histological diagnosis, the patient will be excluded from the study and no sampling will be executed.

3.5 Tissue and blood samples preservation, storage and management

3.5.1. Sampling and analysis

Part 1 – stem cell cultures sampling and processing

Biological samples from patients undergoing surgery for intra-axial brain tumor will be taken and processed. Tumor margins will be collected as well, in order to check tumor resection with histopathological findings and in order to investigate the role of CSCs in the brain adjacent to tumor in determining the tumor recurrence due to resistance to treatments. Both tumor area and its marginal tissue will be taken during the surgery and collected for laboratory procedures and histological analysis. Blood samples will be collected 1-3 days before surgery and 1-3 days after surgery and will be processed for serum collection and stored for further analysis on MVs.

The fresh tissue (tumor and marginal tissues) will be treated in order to obtain single cell suspensions and neurospheres. Then, each patient-derived primary cell cultures will be expanded and subsequently divided into 2 parts: 1) one destined to CSCs cultures for *in vitro* tests; 2) one for biological storage, for further retrospective analyses. The storage of biological samples will be at the Medical Genetics Laboratory ([name]), of School of Medicine and Surgery, University of Milano-Bicocca. All the materials for

STUDY NAME: Vacuolar ATPase and drug resistance of high grade gliomas: a study to investigate possible therapeutic roles for proton pump inhibitors. STUDY CODE: GLIODRUG-V	Ver. 1.0 07/06/2019
---	------------------------

the study will be provided by the same laboratory, so there are no additional costs for the Neurosurgical Division and for Hospital San Gerardo.

Part 2 - in vitro study of drug resistance

Neurospheres from marginal tissues will be obtained by co-culturing of marginal tissue with MVs taken from CSCs cultures medium, in order to better define the role of V-ATPase in drug resistance and the role of MVs in transferring drug resistant phenotypes from a CSCs culture to another.

CSCs cultures will be treated with antineoplastic drugs with and without PPI. In this way, it will be possible to understand the *in vitro* response to antineoplastic agents and PPI.

Anti-neoplastic agents taken into account for this study are: Temozolomide, Vincristine, Carboplatin, Etoposide, Irinotecan (CPT-11), Bevacizumab, BCNU, CCNU, Procarbazine, Irinotecan + Carboplatin, Procarbazine + Vincristine + CCNU (PCV). All these agents have been used for treatment of HGGs as first or second line therapy.

PPIs used for this study are: concanamycin, Bafilomycin-A1, Archazolide-A. All the procedures will be performed for research use at the Medical Genetics Laboratory ([name]), of School of Medicine and Surgery, University of Milano-Bicocca..

Part 3 – serial analysis of blood samples

During the first year of neuro-oncological follow-up, patients will undergo to collection of blood samples pre- and post-operatively, three months, six months, nine months and one year after surgery. Each sample will be processed in order to study the MVs content of subunits of V-ATPase (especially subunit V1G1) and the genetic and epigenetic content (DNA, mRNA and miRNA). The results will be matched with the brain MRIs performed as part of the neuro-oncological follow-up. The blood volume will be of about 5-10 mLs and it will be taken during the normal blood sampling performed during the neuro-oncological follow-up for checking chemotherapy toxicities. No adjunctive invasive procedures will be performed on patients.

During this part of the study, it will be possible to understand the relations between tumor volume and MVs concentrations in the bloodstream in order to understand the role of surgery on the existing vesicular network between the brain and the rest of the body. Moreover, it will be possible to study the effects of adjuvant treatments on the MVs contents during the time of response to treatment and at tumor recurrence. Finally, analysis of DNA, miRNA and mRNA contained in the MVs will allow us to explore the presence of new markers able to predict tumor recurrence and to understand *in vivo* any possible changes of the neoplastic cells during the treatment.

These results will be compared with the results obtained *in vitro* in order to understand if the experimental model can reflect the mechanisms active in the patient.

This part of the research project will allow us to transfer the project from the bench to the bedside and it will be the starting point for future projects.

STUDY NAME: Vacuolar ATPase and drug resistance of high grade gliomas: a study to investigate possible therapeutic roles for proton pump inhibitors. STUDY CODE: GLIODRUG-V	Ver. 1.0 07/06/2019
---	------------------------

MVs isolation will be performed as reported below.

For all patients 20 mL fasting blood sample will be collected in a sterile vacuum tube. The collection will be done in the same time of routine preoperative blood samples or planned follow-up controls, since no others invasive procedure should be required from the patients since their enrollment in the study. The blood sample will be stored at 4°C and handled within 6 hours. Then, 5 mL will be centrifuged at 3000 rpm for 10 minutes at 4°C, the plasma phase will be collected and aliquoted in 1.5 mL sterile tubes and stored at -80°C until use or shipment. Then, we will isolate peripheral blood mononucleate cells (PBMC) through Ficoll gradient from the remaining 15 mL. After isolation, live PBMC will be frozen in standard media 20% Fetal Bovin Serum (FBS) 10% Dymethyl Sulfoxide (DMSO) and stored in liquid nitrogen until use. All these parts of the experiment will be performed at the Medical Genetics Laboratory ([name]), of School of Medicine and Surgery, University of Milano-Bicocca.

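### Section 3.5.1 gives two incompatible volumes for the study blood draw (about 5-10 mL and 20 mL) and two materials, serum and plasma, for the microvesicle samples around surgery

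*Protocol*

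**What the plan says.** Three places in Protocol Section 3.5.1 describe the study blood sample.

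- **Part 1 (stem cell cultures).** "Blood samples will be collected 1-3 days before surgery and 1-3 days after surgery and will be processed for serum collection". The same sentence stores this material for later MV analysis.
- **Part 3 (serial analysis).** Six draws are scheduled: before surgery, after surgery, and at 3, 6, 9 and 12 months. "The blood volume will be of about 5-10 mLs", and it is to be taken with the routine follow-up sampling for chemotherapy toxicity.
- **Isolation procedure (after Part 3).** It opens with "MVs isolation will be performed as reported below" and continues: "For all patients 20 mL fasting blood sample will be collected in a sterile vacuum tube". On timing: "The collection will be done in the same time of routine preoperative blood samples or planned follow-up controls". Of this, 5 mL is centrifuged and "the plasma phase will be collected and aliquoted in 1.5 mL sterile tubes". PBMC are then isolated "through Ficoll gradient from the remaining 15 mL".

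Section 3.7 adds a study blood sample at each neuro-oncological evaluation but gives neither a volume nor a material, so it does not settle the matter.

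**The concern.** There are two contradictions.

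**Volume.** A follow-up draw falls under both Part 3 and the isolation procedure, and the two volumes do not overlap. Staff cannot tell how much blood to take, and at the smaller volume the written PBMC step cannot be carried out.

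**Material.** Part 1 calls for serum around surgery and the isolation procedure calls for plasma. Section 2.1 and Part 3 set out to learn how MV content changes after surgery and during adjuvant treatment, so samples taken around surgery are to be compared with later ones in the same patients. If the earlier samples are serum and the later ones plasma, material is tied to time point in every patient. A difference between time points could then be biological, could come from the material, or both.

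**Working it through.** **1. Volume**

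Inputs, all from Section 3.5.1: 5-10 mL per draw (Part 3); 20 mL per draw, 5 mL for plasma and 15 mL for PBMC (isolation procedure).

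- The procedure's own total: 5 + 15 = 20 mL. It is consistent in itself.
- Ratio of the two volumes: 20/10 = 2 and 20/5 = 4, so 2 to 4 times.
- Left for PBMC after the 5 mL plasma portion: 5 − 5 = 0 mL and 10 − 5 = 5 mL, against 15 mL stated.
- Shortfall: 15 − 5 = 10 mL (10/15 = 67%) to 15 − 0 = 15 mL (100%).

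The 5 mL plasma portion fits within either volume, so the volume conflict does not reach the MV measurement. Reading 5-10 mL as only the MV share of a 20 mL draw does not fit: Part 3 gives it as the volume to be taken, and the procedure spins 5 mL, not 5-10 mL. No total per patient is computed, because the text does not fix how many draws each volume covers.

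**2. Material, draw by draw**

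| Draw | Part 1 | Part 3 | Isolation procedure |
|---|---|---|---|
| Pre-operative | serum | listed, no material given | plasma |
| Post-operative | serum | listed, no material given | not named; covered only by the general opening sentence |
| 3, 6, 9, 12 months | not mentioned | listed, no material given | plasma |

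The serum is not for another purpose: Part 1 says it "will be processed for serum collection and stored for further analysis on MVs". The isolation procedure never mentions serum, and its description of the tube does not give a type that would decide the question.

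**3. What each reading implies**

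- *Each draw follows the text that names it.* The post-operative sample is serum and the follow-up samples are plasma. The pre-operative draw is named by both texts. If it follows the isolation procedure, it is plasma and the comparison across surgery also crosses materials. If it follows Part 1, that comparison is serum to serum, and only comparisons with follow-up cross.
- *The isolation procedure applies to every draw, with or without extra serum around surgery.* Plasma is complete at all six time points and nothing is mixed.

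Under the first reading, let Δ be the true change in MV content between a serum sample around surgery and a plasma sample at follow-up, and δ the plasma-minus-serum difference for the same blood. What is observed is Δ + δ. Every patient has the same material at the same time point, so no contrast within or between patients separates Δ from δ. Neither adjustment nor a larger sample would help. The documents give no value for δ.

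**The case against.** The strongest reply grants both contradictions but disputes their weight.

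On volume, PBMC appear only in the isolation procedure. No objective, Part 3 aim or statistical method uses them, so the shortfall concerns a store with no stated analysis. That stands. The volume conflict leaves the amount of blood and the PBMC store unclear and changes no MV result.

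On material, the isolation procedure is the only one given for MVs from blood, it opens in general terms and it makes no exception. Part 1 has a single sentence on serum, in a part about cell cultures. Part 3 also lists the pre- and post-operative draws under the first year of neuro-oncological follow-up, so the procedure's follow-up controls could include the post-operative draw. On that reading everything is plasma. The reading is possible, but the protocol does not state it, and Part 1 says explicitly that the serum is for MV analysis. If serum was loose wording, it still needs correcting, because staff acting on Part 1 would store serum.

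It is also true that the documents give no evidence that MV content differs between serum and plasma, and that longitudinal change is an aim of Section 2.1 and Part 3 rather than one of the objectives in Section 2.2. Both limit the claim: the mixing is conditional on the reading, and its size is unknown.

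**Conclusion.** Both contradictions hold as written.

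- **Volume:** certain for follow-up draws. The consequence is confined to the amount of blood drawn and the PBMC store.
- **Material:** certain as a conflict for the pre-operative draw, which is assigned to both serum and plasma. For the post-operative draw, serum is stated and plasma follows only from a general sentence. Confounding of material with time point arises if staff follow the text that names each draw. It is limited to comparisons that involve a sample taken around surgery, and no size can be given for it.

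Comparisons among the 3-, 6-, 9- and 12-month samples, the primary in vitro objective and all error-rate and sample-size considerations are untouched. This should be corrected: the remedy is cheap, and once samples have been stored in mixed materials the analysis cannot recover the comparison.

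**What to change.** Reconcile Part 1, Part 3 and the isolation procedure in Section 3.5.1, and align Section 3.7 with the result:

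1. State one blood volume per draw, with a split that adds up to it.
2. State one material for MV analysis at all six time points.
3. Name the post-operative draw in the isolation procedure.
4. If both serum and plasma samples already exist, do not pool them in the longitudinal MV analysis.
5. Check that the consent text, which was not available for this review, gives the same volume.

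The choice of volume and material belongs to the investigators; the documents do not show which was intended. The cost is a few sentences in Sections 3.5.1 and 3.7 and a check of the consent text, with no extra samples or analyses.

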3.5.2 Storage and transport

The biological material will be shipped and stored to the Medical Genetics Laboratory ([name]), of School of Medicine and Surgery, University of Milano-Bicocca the same day of sample collection. No additional costs are required for biological sampling transport since the laboratory is close to the hospital. The biological material will be stored for a maximum period of 10 years.

3.6 Analysis of tumor recurrence

Tumor recurrence will be evaluated according the RANO criteria. Patients will undergo routine neuro-oncological and radiological assessment in order to check the brain and the surgical bed during adjuvant treatments.

3.7 Neuro-Oncological Follow-up

All patients will undergo to a neuro-oncological follow-up. Each patient will be treated with a standard first line treatment according to the Stupp protocol with concomitant chemo-radiation therapy and subsequent adjuvant chemotherapy. Every 3 months, each patient will undergo a brain MRI.

During every neuro-oncological evaluation, each patient will have a blood sample taken in order to check the blood count. During this standard procedure, an additional sample of blood will be taken for this study in order to extract circulating exosomes and DNA.

Brain MRIs will be examined to calculate tumor volumes and residual tumor volumes and to diagnose tumor recurrence.

3.8 Statistical analysis.

Data will be expressed as median and interquartile range (IQR), number and relative percentage, or hazard ratio (HR) with related 95% confidence intervals (CI). Normal distribution of continuous variables will be assessed by Kolmogorov-Smirnov test. To compare baseline characteristics of the groups in the univariate analysis, continuous variables will be analysed using the Mann-Whitney test or ANOVA according to the type of distribution. Categorical variables will be analyzed by Fisher exact test or Chi-Square Test as

STUDY NAME: Vacuolar ATPase and drug resistance of high grade gliomas: a study to investigate possible therapeutic roles for proton pump inhibitors. STUDY CODE: GLIODRUG-V	Ver. 1.0 07/06/2019
---	------------------------

appropriate. A 1:1 propensity-score-analysis, with a caliper of 0.1SD, may be conducted for significant variables ($p < 0.05$) at univariate to reduce the retrospective bias of selection.

Multivariate analysis will be performed by logistic regression analysis or Cox regression as appropriate. DFS, OS and TSS will be evaluated by Kaplan-Meier method. Comparison between groups will be performed with the log-rank test. A Receiver Operating Characteristic (ROC) curve analysis will be employed as appropriate. The optimal cut-off value will be established based on the Youden index. All statistics will be 2-tailed and statistical significance will be accepted when $p < 0.05$.

3.9 Data management.

Data will be stored in an electronic database. Each investigator may have access to the whole dataset.

The subject will be identified by an alphanumeric code linked to the name of the patient that the enrolling investigator can see. Appropriate measures such as encryption or deletion will be enforced to protect the identity of human subjects in all presentations and publications as required by local/regional/national requirements. During the patients entering in the database, data quality will be ensured. At least one report analysis will be performed each year.

Major protocol deviations will lead to exclusion of data from the analysis, while data will not be excluded because of minor protocol deviations. The list of major protocol deviations will be detailed and documented in the clean file document prior to database release.

The personal data subject of the study will be processed in compliance with the European Regulation on the Protection of Personal Data (GDPR), of Legislative Decree 196/2003 and subsequent amendments and additions, and of any other Italian law applicable to the protection of personal data (hence referred to as "applicable data protection law").

With regard to personal data made available to the Promoter in a pseudo-anonymized form, the Institute and the Promoter are considered joint owners, each for their own area of competence, and both will act in compliance with the applicable data protection law.

Furthermore, the Institute and the Promoter will cooperate to take the necessary measures to comply with the applicable data protection law, and will also have to implement appropriate technical and organizational measures to guarantee the GDPR compliance requirements.

The Institute is responsible for providing its Principal Investigators and Research Personnel with all necessary information concerning the methods through which the Promoter will eventually collect and manage their personal data before such information is provided.

The Promoter ensures the correctness of the processing of personal data as provided by the GDPR. If the user becomes aware of a data breach of personal data, the user himself must promptly notify the other users of this event, and in any case no later than 24 hours from the knowledge of the event. In this case, the user will have to cooperate fully with the other users to remedy the data breach, fulfilling the mandatory notification within the set times and managing any damage caused.

The data breach of personal data is defined by the art. 33 and 34 of the GDPR.

The roles and responsibilities related to the project will be explained in a further and separate act between the Promoter and the institute.

STUDY NAME: Vacuolar ATPase and drug resistance of high grade gliomas: a study to investigate possible therapeutic roles for proton pump inhibitors. STUDY CODE: GLIODRUG-V	Ver. 1.0 07/06/2019
---	------------------------

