2.3 Type of Study

This is a prospective observational cohort study on biological materials.

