2.4 Study Population

Planned number of subjects undergoing surgical removal of intra-axial brain tumor at the Neurosurgical Division of Ospedale San Gerardo: almost 45 per year. Thirty patients are expected to have a glioma of which 25 patients are expected to be diagnosed with a GBM and 5 with a LGG. We plan to enroll 25 patients/year.

STUDY NAME: Vacuolar ATPase and drug resistance of high grade gliomas: a study to investigate possible therapeutic roles for proton pump inhibitors. STUDY CODE: GLIODRUG-V	Ver. 1.0 07/06/2019
---	------------------------

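### The optional propensity match picks its covariates by univariate p<0.05; with about 50 patients this often leaves real confounders out and discards a large share of the cohort

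*Protocol*

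**What the plan says.** Section 3.8 of the protocol first compares baseline characteristics between groups with univariate tests: Mann-Whitney or ANOVA for continuous variables, Fisher or chi-square for categorical ones. It then adds: "A 1:1 propensity-score-analysis, with a caliper of 0.1SD, may be conducted for significant variables" (p<0.05), and gives the purpose as "to reduce the retrospective bias of selection". The next sentence commits to multivariable logistic or Cox regression. The section does not define the groups to be matched or say which quantity the SD belongs to.

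Section 2.3 describes the design: "This is a prospective observational cohort study on biological materials". Section 2.4 says "We plan to enroll 25 patients/year", and section 2.7 gives "Duration for enrollment: 24months" and "Duration for follow-up analysis: 12 months for each patient". No total sample size is stated.

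**The concern.** The rule fixes how confounders enter the matched analysis, and it does so by significance of the baseline difference. In a small cohort, non-significance mostly reflects lack of power. A factor that is truly imbalanced and strongly prognostic can fail the screen, while an imbalanced factor with no bearing on outcome passes it. Matching 1:1 within a narrow caliper then removes patients from a cohort that is already small.

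If a patient-level comparison were built this way (for example, survival by level of V-ATPase expression, which is only an illustration), it would lose precision and could keep the confounding that the matching was meant to remove. No trigger is given for doing or omitting the match, so the choice could follow the results.

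**Working it through.** The protocol gives no power, sample-size or matched-sample figure, so there is nothing of its own to reproduce.

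**Cohort size.** 25 patients a year (section 2.4) × 2 years (section 2.7) = 50. Withdrawals and exclusions would lower this.

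**Chance that the screen flags a truly imbalanced continuous variable.** Two-sided 0.05, imbalance of d standard deviations, normal approximation: power ≈ Φ(d·√(n₁n₂/(n₁+n₂)) − 1.96). The splits and values of d are assumptions.

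| Split | √(n₁n₂/50) | d = 0.3 | d = 0.5 | d = 0.8 |
|---|---|---|---|---|
| 25 / 25 | 3.54 | 18% | 42% | 81% |
| 17 / 33 | 3.35 | 17% | 39% | 76% |
| 10 / 40 | 2.83 | 13% | 29% | 62% |

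Worked case, 25/25 and d = 0.5: 0.5 × 3.54 − 1.96 = −0.19, and Φ(−0.19) ≈ 0.42. For a binary factor at 30% versus 50%, the power at 25/25 is about 30%.

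**Several confounders together.** Simulation, 800 runs at 25/25, with six truly imbalanced variables (four continuous at 0.5 SD, two binary at 42% versus 30%): on average 4.3 of the 6 were missed, and in 12% of runs none was selected.

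**Loss forced by 1:1 matching alone.** At most twice the smaller group is kept. The loss is 0% at 25/25, 20% at 20/30 (40 kept), 32% at 17/33 (34 kept) and 60% at 10/40 (20 kept). Losing more than half is certain only if 2 × the smaller group is below 25, that is, 12 patients or fewer.

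**Loss with the caliper added.** Simulation at N = 50 with matching without replacement. The caliper was assumed to be 0.1 SD of the logit of the score. The figures are for data sets in which at least one variable passed the screen; the means are for greedy nearest-neighbour matching.

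| Selected variables | Split | Mean loss |
|---|---|---|
| One binary | 25/25; 17/33 | 41%; 44% |
| One continuous | 25/25 | 50–54% |
| One continuous | 17/33 | 56–59% |
| Those significant among six | 25/25 | 51–69% |
| Those significant among six | 17/33 | 57–73% |
| Those significant among six | 10/40 | 71–80% |

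The chance of losing more than half was 12% (25/25) or 20% (17/33) with one binary variable. With one continuous variable at 25/25 it was 45–68% for greedy matching and 35–58% for the best possible matching. A separate simulation, with three confounders of 0.5, 0.8 and 1.2 log-odds per SD, kept 22.8, 20.9 and 17.8 of 50 patients on average, a loss of 54%, 58% and 64%.

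**Type I error.** In simulations with assumed confounder effects on the outcome (0.3 to 0.5 SD), screening and matching rejected a true null in about 6–12% of data sets. A full-cohort model containing exactly the true confounders rejected in about 4–6%. That comparator is idealised.

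**Events available for regression.** The protocol's introduction gives a median survival of 14–16 months for glioblastoma after gross total resection and adjuvant chemo-radiation. Assume exponential survival, apply this to all 50 patients, and follow each for 12 months:
- median 14: 50 × (1 − 2^(−12/14)) = 50 × 0.448 = 22.4 deaths
- median 16: 50 × (1 − 2^(−12/16)) = 50 × 0.405 = 20.3 deaths

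At the conventional 10 events per parameter, 20–22 deaths support about two parameters, one of which is the exposure.

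**The case against.** The best defence is that the match is optional while regression on the full cohort is planned outright. A reader might infer that matching is the plan's only control for confounding, so that the adjusted result would rest on about 20 patients. The text does not support that: the sentence on logistic and Cox regression follows directly, and it discards nobody.

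A reader might also conclude that more than half the cohort would certainly be lost. That depends on the group split, on the number and type of variables selected, and on the caliper scale, none of which the protocol gives; with one binary variable the mean loss is nearer 40%. Nor can a particular type I error be attributed to this plan, because it depends on outcome effects that the documents do not supply and because the planned regression was not what was simulated.

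The primary objective (section 2.2) is in vitro, section 3.5.1 compares inhibitors in cultures, and section 3.7 assigns all patients the same first-line regimen. Matching could therefore touch only patient-level comparisons. Finally, selection bias also arises in prospective cohorts, and section 3.5.1 foresees retrospective use of stored samples, so that word is a minor matter.

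All of this limits the reach of the point. It does not rescue the selection rule, which the protocol writes out and which performs poorly at this sample size. Nor can the rule be excused as detail left to an analysis plan, since ratio, caliper and selection threshold are all fixed here.

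**Conclusion.** The concern stands in limited form and should be acted on. Choosing propensity covariates by univariate p<0.05 in about 50 patients misses a moderate true imbalance (0.3–0.5 SD) more often than it finds it: detection is about 18–42% with equal groups and 13–29% at 10 versus 40. It also takes no account of prognosis. If the match were done, roughly 40–80% of patients would be discarded on average, often more than half. These figures rest on the derived total of 50, on assumed splits and imbalances, and, for the loss, on a caliper taken on the logit scale. Inflation of the type I error is possible, and its size is open. The damage is confined to optional patient-level comparisons.

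**What to change.** Delete the sentence on p<0.05-selected matching. Make the regression already planned in section 3.8, on the full cohort, the adjusted analysis, with a short covariate list named in advance from data already collected, such as age, Karnofsky status, extent of resection, and grade or molecular class.

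Size the list to each endpoint's expected events. For overall survival, about two parameters including the exposure leave room for one covariate, unless penalised regression is used; progression may allow more. If a propensity score is kept, build it on the same fixed list, use weighting that retains all patients, and label it a sensitivity analysis. Replace the reference to retrospective selection bias with wording that fits the prospective design in section 2.3.

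The cost is a few lines in section 3.8 and no new data. The drawback is that the covariates must be chosen before the data are seen, so a factor that turns out to be imbalanced can be added only as a declared exploratory analysis.
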